6.6.6.5 Cardiac Findings

AZD0466 should be withheld if any of the following occur at any time during study intervention:

- Symptomatic tachycardia
- Symptomatic hypotension
- QTcF shortening by 60 milliseconds compared to baseline, or interval value < 340 milliseconds, confirmed on at least 2 separate ECGs recorded 5 minutes apart
- QTcF prolongation of > 500 milliseconds or QTcF prolongation from baseline by 60 milliseconds, confirmed on at least 2 separate ECGs recorded 5 minutes apart
- Any other cardiac findings of CTCAE Grade ≥ 2 or considered by the Investigator to be clinically significant.
- AZD0466 should be permanently discontinued if a CTCAE Grade ≥ 3 cardiac AE of any duration occurs during study intervention, if considered by the Investigator to be related to study intervention.

Further investigation of the cardiac findings should be considered, including referral to a cardiac specialist. Patients should be monitored closely. AZD0466 may be restarted after resolution of cardiac findings to the patient's baseline at the discretion of the Investigator and after discussion with the Study Physician.

6.6.6.6 Infusion Site Reactions

As with other drugs administered intravenously, local infusion site reactions (eg infusion pain, infusion site reaction, skin irritation, or vein irritation) may occur. For CTCAE Grade ≥ 2 reactions, the infusion of AZD0466 should be stopped; if the patient recovers without issue, a full dose may be considered at the next scheduled infusion. For CTCAE Grade 1 or transient reactions with recovery within 15 minutes, AZD0466 infusion may be restarted if timings permit it to be completed within the 3-hour window of stability.

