Infusion site reactions	As with other drugs administered intravenously, local infusion site reactions (eg, infusion pain, infusion site reaction, skin, or vein irritation) may occur.	These reactions can be managed according to local institutional guidelines. Implantable port insertions (eg, Portacath) may be considered.

CSP = clinical study protocol.

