6.6.6.1 Dose Modifications

AZD0466 may be withheld and the dose reduced due to haematologic or non-haematologic toxicities. In general, no AZD0466 dose modification is required if a patient experiences a Grade 1 or Grade 2 AEs. However, AZD0466 treatment should be modified or discontinued when the AEs described in this section are observed.

AZD0466 dose modification is at the discretion of the Investigator. However, some considerations have been provided.

- For platelet and liver changes, consider Q2W ([Table 6](#)) and at second occurrence, consider triggering dose reductions ([Table 7](#)).
- For AEs other than platelet and liver-related toxicities, consider reducing the dose ([Table 7](#)).
- Dose modifications can be done in two ways, which include dose reduction and frequency change (from weekly to bi-weekly schedule). Frequency changes are not possible during ramp-up. A maximum of 3 dose modifications is acceptable, except for CTCAE Grade 3 or 4 haemorrhage and any intracranial haemorrhage or haematoma, of which only one event is allowed. See [Table 8](#), [Table 9](#), [Table 10](#), and [Table 11](#).

Table 6

Dose Frequency Changes

CCI

[figure not shown]
[figure not shown]

Table 7

Dose Reduction Modifications

CCI

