6.6.6.3 Dose Modifications Based on Non-haematologic Parameters

Dose modifications for non-haematologic toxicities may occur at any time and the management are shown [Table 9](#). Special considerations for TLS and specific AEs are included in [Appendix F](#).

Dose modifications for changes in hepatic biochemistry are summarised in Section [6.6.6.4](#).

If a patient experiences a clinically significant and/or unacceptable non-haematologic toxicity (including a DLT), considered by the Investigator to be related to study intervention, and not attributable to the disease (or to disease-related processes) under investigation, dosing will be withheld or the dose reduced and supportive therapy administered as required.

Table 9 Dose Modifications for Non-haematologic Toxicities

Event	Occurrence	Action with AZD0466
Non-haematologic toxicities (except hepatic and cardiac changes, see Sections 6.6.6.4 and 6.6.6.5)		
CTCAE Grade 1 non-haematologic toxicities	Any	None
CTCAE Grade 2 non-haematologic toxicities	First occurrence	None
	Second occurrence	
 Withhold AZD0466 until resolution to CTCAE Grade ≤ 1 or baseline. Maximum dose hold 21 days Restart AZD0466 at same dose level Discontinue AZD0466 if no resolution to CTCAE Grade ≤ 1 or baseline in ≤ 21 days
	On third and subsequent occurrences	
 Withhold AZD0466 until resolution to CTCAE Grade ≤ 1 or baseline. Maximum dose hold 21 days Restart AZD0466 at one lower dose (Table 7). A maximum of 3 dose reductions is permitted Discontinue AZD0466 if no resolution to CTCAE Grade ≤ 1 or baseline in < 21 days
CTCAE Grade 3 non-haematologic toxicities	First occurrence	
 Withhold AZD0466 until resolution to CTCAE Grade ≤ 1 or baseline Supportive therapy should be given as per institutional guidelines If resolution occurs in ≤ 7 days, restart AZD0466 at the same dose level, after discussion with Study Physician If no resolution in ≤ 7 days, withhold AZD0466 for up to a total of 21 days If resolution occurs in > 7 days but ≤ 21 days, restart AZD0466 at one lower dose (Table 7) Discontinue AZD0466 if no resolution to CTCAE Grade ≤ 1 in < 21 days

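### The infusion site reaction rule leaves a full dose open after severe drug-related reactions for which Table 9 says stop or reduce, and no text ranks the two

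*Protocol*

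**What the plan says.** **Section 6.6.6.6.** The infusion is stopped for a Grade 2 or higher infusion site reaction. After that, "if the patient recovers without issue, a full dose may be considered at the next scheduled infusion". The section names no highest grade, does not distinguish a first reaction from a repeat, and does not mention Table 9.

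**Section 6.6.6.3 and Table 9.** The text applies to "clinically significant and/or unacceptable non-haematologic toxicity (including a DLT), considered by the Investigator to be related to study intervention". The scope line of Table 9 reads "Non-haematologic toxicities (except hepatic and cardiac changes, see Sections 6.6.6.4 and 6.6.6.5", so hepatic and cardiac changes are its only exceptions. The introduction adds: "Special considerations for TLS and specific AEs are included in" Appendix F. That appendix deals with tumour lysis syndrome, thrombocytopenia and haemorrhage, neutropenia and anaemia. It has nothing on infusion site reactions.

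**Section 6.6.6.1.** Two sentences pull in different directions: "AZD0466 dose modification is at the discretion of the Investigator. However, some considerations have been provided", and "AZD0466 treatment should be modified or discontinued when the AEs described in this section are observed".

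**Section 6.6.7.** Resumption of treatment is referred to Section 6.6.6, with Tables 8 to 11 named in brackets. The Study Physician is to be contacted for situations that the protocol does not cover.

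**Section 2.3.1, Table 1.** Infusion site reactions are listed under study procedures: "These reactions can be managed according to local institutional guidelines. Implantable port insertions (eg, Portacath) may be considered".

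**The concern.** A Grade 4 or repeat Grade 3 local reaction that the Investigator attributes to AZD0466 falls under both sections. One leaves re-dosing at the full dose open once the patient has recovered. The other says stop, or go down one dose. An Investigator who opens Section 6.6.6.6, the section named for the event, finds no sign that a stricter rule may apply.

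What is at stake is patient safety on re-exposure after a severe reaction, and consistent handling across sites. Sample size, error rates and the planned analyses are not affected.

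**Working it through.** There is no figure in the plan to reproduce. The check sets the two rules side by side for a reaction considered related to AZD0466, and then looks for text that ranks them.

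**Step 1: row by row.** Table 9 has six grade-by-occurrence rows at Grade 2 or higher. Against each, Section 6.6.6.6 offers the same option: a full dose may be considered after recovery.

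| Table 9 row | Table 9 action | Against the full-dose option |
|---|---|---|
| Grade 2, first | No change | Compatible |
| Grade 2, second | Hold, then same dose | Compatible |
| Grade 2, third or later | Hold, then "Restart AZD0466 at one lower dose (Table 7). A maximum of 3 dose reductions is permitted" | Differs, but which rule is better is a design choice |
| Grade 3, first | Resolved in ≤ 7 days: same dose after Study Physician discussion. Resolved in > 7 to ≤ 21 days: one lower dose | Differs in part |
| Grade 3, second or later | One lower dose; discontinue if not at Grade ≤ 1 in ≤ 21 days | Differs |
| Grade 4, any | Discontinue | Differs |

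Count: 2 differ + 1 differs in part + 1 design choice + 2 compatible = 6.

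**Step 2: can the first-Grade-3 case arise?** Section 6.6.6.6 looks to the next scheduled infusion, so the patient must have recovered by then. On weekly dosing at nominal days that means within 7 days, and Table 9 then also allows the same dose. The rules part only if the gap exceeds 7 days. With the ± 2-day window in Tables 13 and 14:

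- Weekly, earlier infusion on its nominal day: 7 + 2 = 9 days at most.
- Weekly, earlier infusion 2 days early: 7 + 4 = 11 days at most.
- Every 2 weeks: 14 days nominal, 14 + 2 = 16 or 14 + 4 = 18 days at most.

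So this case arises only when a weekly infusion falls late or the patient is on the 2-weekly schedule. It is secondary to the two rows that differ outright.

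**Step 3: is there an exception or a ranking?**

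- The Table 9 scope line does not except infusion site reactions, and Appendix F does not cover them.
- Section 6.6.6.1 gives general discretion and does not order the two rules.
- Section 6.6.7 names Tables 8 to 11, which leans towards Table 9. It does so under a reference to the whole of Section 6.6.6, which contains 6.6.6.6. Its Study Physician route is for uncovered situations, and this one is covered twice.
- Table 1 mentions local guidelines and ports, without a grade limit.
- The Module 1 dose modification and resumption sections (10.6.6.7 and 10.6.6.8) refer back to the core text.

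No explicit order was found.

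**The case against.** The strongest reply is that the texts do not contradict each other. Section 6.6.6.6 gives a conditional permission, so an Investigator who follows Table 9 complies with both sections. One who gives a full dose after a drug-related Grade 4 reaction departs from Table 9. Section 6.6.7 points the same way. This stands, and it rules out a stronger reading: a reader might infer that the protocol requires, or clearly authorises, full-dose re-challenge after Grade 4. The documents do not say that. They leave the option open in one place and close it in another.

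A second reply is that these are local, procedural events. Table 1 lists them under study procedures, apart from infusion related reaction, which it lists as a potential risk of the drug. A short rule of their own is reasonable. This also stands, and reactions judged unrelated to AZD0466 are outside the point. It does not settle the related ones, because Table 9 is not limited to systemic toxicity.

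A third reply is that other safeguards exist. In Cycle 1 a Grade 4 non-haematologic toxicity, or a Grade 3 lasting more than 7 days, meets the DLT definition subject to its listed exceptions, and is reported to the Study Physician within 24 hours (Section 10.6.6.3). Section 7.1 stops treatment for an adverse event judged to contraindicate further dosing, and Section 8 sends immediate safety concerns to the Sponsor. These make silent re-dosing less likely. None states the dose to resume, and the DLT period ends with Cycle 1.

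Finally, full dose might mean a complete infusion at whatever level applies. That would ease the Grade 3 rows, but it would still not fit discontinuation for Grade 4.

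**Conclusion.** The point holds as an unranked overlap. Read as written, Section 6.6.6.6 leaves a full dose open after a drug-related Grade 4 or a second or later drug-related Grade 3 infusion site reaction, where the protocol's own toxicity table says discontinue or reduce. That is two of six rows, plus the first-Grade-3 row in part. The row count describes how far the rules overlap; it does not measure harm. The documents give no frequency, and severe local reactions that are related and also recover before the next infusion may be few.

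A reader might also count the third Grade 2 reaction as a safety defect. The documents do not support that: Table 1 suggests a port, and for recurrent local irritation that may be more sensible than a lower dose. It needs a stated choice.

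The conclusion assumes that the Investigator relates the reaction to AZD0466 and that the Table 9 scope line is complete as printed. The change is worth making for patient safety because it is small.

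**What to change.** 1. In Section 6.6.6.6, limit the full-dose sentence to Grade 2 reactions.
2. Add: *For Grade ≥ 3 infusion site reactions considered related to AZD0466, follow Table 9 in full, including its resolution limits and Study Physician discussion.* Referring to the table as a whole keeps its 21-day limits and its clinical-benefit condition for repeat Grade 3 events that take more than 7 days to resolve.
3. State in the same section that it, and not Table 9, governs Grade 2 infusion site reactions, for example by considering an implantable port for recurrences.
4. Add to the Table 9 scope line: *Grade 2 infusion site reactions, see Section 6.6.6.6.*

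Add no new rule for reactions judged unrelated. Investigator judgement, local guidelines and the existing Study Physician contact in Section 6.6.7 remain for those.

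Cost: a few sentences in one section and one phrase in a table, which can go into the next amendment. The SAP does not change and no new data are needed, because the Investigator's causality rating is already collected for every adverse event (Section 8.3.2). The downside is slightly less Investigator flexibility after severe local reactions.

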6.6.6.7 Progressive Disease

Permanently discontinue AZD0466 in the absence of clinical benefit after discussion with the Study Physician ([Appendix J](#)).

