been determined, Part B may open to further explore the preliminary anticancer efficacy of AZD0466 monotherapy in patients with selected lymphoid malignancies, including R/R MCL (Cohort B1), R/R FL or MZL (Cohort B2), and R/R DLBCL (Cohort B3).

An SRC (Appendix [A 5](#)) will review emerging data from evaluable patients in each cohort in Module 1 to monitor safety data on an ongoing basis.

This protocol has a modular design with the potential for future treatment arms to be added, as described in Section [4.1.4](#).

Disclosure Statement:

This is a non-randomised, open-label, dose escalation and expansion study.

Number of Patients:

In Module 1 Part A, a minimum of ~~cc1~~ patients will be enrolled in a dose cohort and evaluated through the DLT evaluation period of 28 days before a dose escalation/dose expansion/de-escalation decision can be made (unless unacceptable toxicity is encountered prior to enrolment of ~~cc1~~ patients). The maximum number of patients at any given dose cohort will be capped at ~~cc1~~ patients.

In Module 1 Part B, up to ~~cc1~~ patients will be enrolled (~~cc1~~ patients for Cohort B1 and for Cohort B2, and ~~cc1~~ patients for Cohort B3).

Intervention Groups and Duration:

All patients will receive AZD0466. Treatment will continue for 2 years or until disease progression, initiation of alternative anticancer therapy, unacceptable toxicity, withdrawal of consent, or other reasons to discontinue study intervention, whichever occurs first. For patients who are responding and do not experience unacceptable toxicities, continuation of treatment may be considered by the Investigator and Sponsor.

Patients in Module 1 will receive AZD0466 monotherapy. Patients enrolled into subsequent modules incorporated via protocol amendment may receive AZD0466 in combination with other anticancer treatments.

Data Monitoring Committee:

This study will utilise an SRC, as described in Appendix [A 5](#).

[figure not shown]
Statistical Methods:

Refer to the relevant individual modules for statistical considerations in this study.

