7 DISCONTINUATION OF STUDY INTERVENTION AND PATIENT DISCONTINUATION/WITHDRAWAL – CORE

7.1 Discontinuation of Study Intervention

It may be necessary for a patient to permanently discontinue study intervention. If study intervention is permanently discontinued, patients will continue to have follow-up assessments per the SoA.

Note that discontinuation from study intervention is NOT the same thing as withdrawal from the study.

Patients will be permanently discontinued from study intervention if the following criteria are met:

- Patient decision. The patient is at any time free to discontinue study intervention, without prejudice to further treatment. A patient who discontinues study intervention is normally expected to continue to participate in the study (eg, for safety and survival follow-up) unless they specifically withdraw their consent to all further participation in any study procedures and assessments.
- Investigator decision.
- Occurrence of any AE that, in the opinion of the Investigator or AstraZeneca contraindicates further dosing.
- Pregnancy or intent to become pregnant.
- Patients incorrectly initiated on study intervention. When the reason does not impact safety, consider the risk/benefit to the patient of stopping treatment.
- Noncompliance with the CSP that, in the opinion of the Investigator or AstraZeneca, warrants withdrawal from study intervention (eg, refusal to adhere to scheduled visits).
- The discovery of an unexpected, significant, or unacceptable risk to the patients enrolled in the study.
- Decision to modify the development plan of the drug.
- Initiation of alternative anticancer therapy including another investigational agent.
- Confirmed disease progression ([Appendix J](#)).
- Death.

All patients who are discontinued from study intervention should complete protocol-specified procedures for discontinuation of study intervention and follow-up procedures. Discontinued patients will be followed for survival, either through direct contacts or by collecting public records (eg, death certificates) as allowed by local laws.

The EoT visit should be performed as soon as the patient is permanently discontinued from study intervention. The reason for discontinuation should be documented in the source document and the appropriate section of the eCRF.

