10.4.1 Overall Design

Module 1 will evaluate the safety, tolerability, PK, and efficacy of AZD0466 as monotherapy. Module 1 comprises 2 parts: AZD0466 monotherapy dose escalation in patients with advanced B-NHL (Part A) followed by 3 independent dose expansion cohorts of patients with defined lymphoid malignancies (Part B). The Module 1 schema is illustrated in [Figure 2](#).

- **Part A:** Phase 1 dose setting to assess the safety and tolerability and determine dose(s) and schedule(s) to be evaluated in Part B.
- **Part B:** Phase 1b/2a dose expansion to assess the efficacy of AZD0466 in 3 select patient populations: R/R MCL (Cohort B1), R/R FL or MZL (Cohort B2), and R/R DLBCL (Cohort B3).

An SRC will be responsible for making recommendations for dose escalation or dose de-escalation decisions after each dose level. The SRC will also assess all evaluable patients to establish the RP2D and determine if the study should progress to Part B. Refer to [Appendix A 5](#) for details of the SRC.

Treatment will be administered in the outpatient setting with close monitoring. All patients will be treated until progressive disease or unacceptable toxicity or withdrawal of consent. All patients should be followed for survival every 3 months until death. Patients who discontinue treatment due to unacceptable AEs should be followed until resolution or stabilisation of the AE, then for response and survival. Patients who achieve a CR will be followed for relapse of disease until death.

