10.6.6.2 Dose Expansion

Cohorts may open either in parallel or sequentially at the Sponsor's discretion. The dose expansion part of the study (Part B) will enrol up to approximately [redacted] patients. After determining the RP2D in Module 1 Part A (dose escalation), the following separate cohorts may be opened at the RP2D in Module 1 Part B.

- **Cohort B1:** Approximately [redacted] response-evaluable patients with R/R MCL
- **Cohort B2:** Approximately [redacted] response-evaluable patients with R/R FL or MZL
- **Cohort B3:** Approximately [redacted] response-evaluable patients with R/R DLBCL

Following an initial ramp-up during Week 1, AZD0466 will be administered based on a weekly dosing schedule for 2 years or until disease progression, initiation of alternative anticancer therapy, unacceptable toxicity, withdrawal of consent, or other reasons to discontinue study intervention, whichever occurs first. In the event of liver or haematologic toxicities, a 2-weekly dosing schedule may be considered. In the absence of toxicities, a 2-weekly dosing schedule may also be considered after discussion with the Sponsor. For patients who are responding and do not experience unacceptable toxicities, continuation of treatment may be considered by the Investigator and Sponsor.

All patients should be followed for survival every 3 months until death. Patients who discontinue treatment due to unacceptable AEs should be followed until resolution or stabilisation of the AE, then for response and survival. Patients who achieve a CR will be followed for relapse of disease until death.

If the interim analysis of Part B meets the pre-set target value for monotherapy expansion in Cohorts B1 and B2, additional patients will be enrolled in these cohorts.

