Appendix J New York Heart Association Functional Classification

Class	Patient Symptoms	Class	Objective Assessment
I	No limitation of physical activity. Ordinary physical activity does not cause undue fatigue, palpitation, dyspnea (shortness of breath).	A	No objective evidence of cardiovascular disease. No symptoms and no limitation in ordinary physical activity.
II	Slight limitation of physical activity. Comfortable at rest. Ordinary physical activity results in fatigue, palpitation, dyspnea (shortness of breath).	B	Objective evidence of minimal cardiovascular disease. Mild symptoms and slight limitation during ordinary activity. Comfortable at rest.
III	Marked limitation of physical activity. Comfortable at rest. Less than ordinary activity causes fatigue, palpitation, or dyspnea.	C	Objective evidence of moderately severe cardiovascular disease. Marked limitation in activity due to symptoms, even during less-than-ordinary activity. Comfortable only at rest.
IV	Unable to carry on any physical activity without discomfort. Symptoms of heart failure at rest. If any physical activity is undertaken, discomfort increases.	D	Objective evidence of severe cardiovascular disease. Severe limitations. Experiences symptoms even while at rest.

Source: <https://www.heart.org/en/health-topics/heart-failure/what-is-heart-failure/classes-of-heart-failure> adapted from Dolgin M, Association NYH, Fox AC, Gorlin R, Levin RI, New York Heart Association. Criteria Committee. Nomenclature and criteria for diagnosis of diseases of the heart and great vessels. 9th ed. Boston, MA: Lippincott Williams and Wilkins; March 1, 1994.

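### Protocol 6.6.6.7 makes the stop at progression conditional on lack of clinical benefit, Section 7.1 makes it mandatory once progression is confirmed, and both cite the wrong appendix

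*Protocol*

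**What the plan says.** Protocol 6.6.6.7, headed Progressive Disease, is one sentence: "Permanently discontinue AZD0466 in the absence of clinical benefit", with the proviso that this follows a discussion with the Study Physician, and a reference to Appendix J.

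Protocol 7.1 opens its list with "Patients will be permanently discontinued from study intervention if the following criteria are met". One item is "Confirmed disease progression", again with a reference to Appendix J. That item carries no exception for benefit.

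The treatment-duration statements agree with each other and also carry no such exception:
- Synopsis: "Treatment will continue for 2 years or until disease progression, initiation of alternative anticancer therapy, unacceptable toxicity".
- Section 10.4.1: "All patients will be treated until progressive disease or unacceptable toxicity or withdrawal of consent".
- Section 10.6.6.2, for Part B: "for 2 years or until disease progression, initiation of alternative anticancer therapy, unacceptable toxicity".
- SAP 8.2 gives the same rule as 10.4.1.

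The synopsis and 10.6.6.2 do let the Investigator and Sponsor consider continuing treatment, but only for patients who are responding.

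The appendix that 6.6.6.7 and 7.1 point to is "Appendix J New York Heart Association Functional Classification". The lymphoma response criteria, including progression, are in Appendix K.

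**The concern.** A site with a patient who has progressed but seems to be doing well finds two answers. The section on dose modification suggests that the drug may go on after a conversation with the Study Physician. The section on discontinuation says it must stop once progression is confirmed. Neither section mentions the other, and the appendix both cite says nothing about progression, confirmation or benefit.

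The date of last dose is at stake, with everything computed from it: exposure, the period in which AEs count as treatment-emergent, and whether continued dosing is recorded as a departure from the dosing regimen. If sites resolve the conflict differently, these summaries mix two dosing policies.

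**Working it through.** No figure in the plan is at issue, so the check compares the texts and then traces what depends on the date of last dose.

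**Step 1. The stopping rules side by side.**

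| Place | Trigger | Benefit exception |
|---|---|---|
| Protocol 6.6.6.7 | Progression (from the heading) without clinical benefit | Implied |
| Protocol 7.1 | Confirmed progression | None |
| Protocol synopsis | Progression | None |
| Protocol 10.4.1 | Progression | None |
| Protocol 10.6.6.2 | Progression | None |
| SAP 8.2 | Progression | None |

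One place makes the stop conditional and five do not. Only 7.1 asks for confirmation. Section 7.1 does qualify another item in its list: for patients started on drug in error, risk and benefit are to be weighed where safety is not affected. The list therefore states a qualification where one is meant, and it states none for progression.

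**Step 2. The cross-reference.** Appendix J holds the cardiac classes. Exclusion criterion 11 in Section 5.2 cites it correctly for that purpose. Section 8.1.3.1 correctly sends response assessment to Appendix K. The references in 6.6.6.7 and 7.1 are therefore wrong. Redaction and text extraction do not explain this, because the list of appendices shows the same titles.

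**Step 3. Whether Appendix K supplies the missing definition.** Only in part. K 2 asks for confirmation by another modality when FDG uptake rises at a previously unaffected site, and Table K35 allows a biopsy or interval scan for an uncertain new lesion. Neither is a general rule for confirming progression, and Appendix K does not define clinical benefit for this purpose.

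**Step 4. Who is affected.** A progressing patient without benefit stops under 6.6.6.7 and, once progression is confirmed, under 7.1. The sections give different answers only for a progressing patient judged to benefit. The documents give no count or expected proportion for that group.

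**Step 5. Which quantities move.** Let L be the date of last dose if drug stops at progression, and x the extra days of dosing if it does not.

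- *Exposure* (Protocol 9.4.1, SAP 5.6.1.1) is counted from the last dose, so it grows with x.
- *Treatment-emergent window* (Protocol 9.4.3.1, SAP 5.6.2.1) ends at the earlier of last dose + 30 days and the day before subsequent therapy. With no subsequent therapy, the end moves from L + 30 to L + x + 30. As an illustration, one extra 28-day cycle of weekly dosing is 28/7 = 4 more doses and x = 28, so the window ends at L + 58.
- *Cycle 2 onwards events* meeting the DLT criteria at the RP2D (SAP 11.1.9.2), and the pooled safety data behind a recruitment pause (Protocol 4.5), can include events from the extra dosing.
- *Dosing deviation* (SAP 4.3.7, Deviation 4): the same doses may be a deviation under 7.1 and not under 6.6.6.7.
- *OS* is defined regardless of treatment withdrawal or later therapy (SAP 5.2.6.1), so its derivation does not change. Only an indirect effect is possible, for instance through the timing of the next therapy.

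**Step 6. Which quantities do not move.** ORR and best response use data only up to progression (Protocol 9.4.2, SAP 5.2.1.1). DoR and PFS end at progression (SAP 5.2.3.2, 5.2.5.1). Treatment status at progression (Protocol 9.4.2, SAP 5.2.5.3) is fixed on the progression date, so later dosing cannot alter it.

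One further gap follows. Efficacy assessments stop at progression (Protocol 8.1.2), so a patient continued under 6.6.6.7 would have no scheduled imaging on which to judge continuing benefit.

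**The case against.** The strongest defence is that this is one loosely worded line against a consistent rule. No sentence expressly says that dosing may continue after progression; 6.6.6.7 says only when to stop. Section 7.1 is the dedicated discontinuation section, its wording is mandatory, and four other places agree with it. This stands as far as it goes. A reader might infer that the protocol openly permits what it elsewhere forbids, and the documents do not support that: the permission is an implication. But under a heading about progressive disease, a condition about benefit has no function unless some progressing patients may continue, so the implication is hard to avoid.

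A second defence is that 6.6.6.7 covers equivocal progression and 7.1 covers confirmed progression. The partial confirmation steps in Appendix K make this plausible. Neither section says so, however, and no general meaning of confirmed is given. The reading softens the conflict without removing it.

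Third, discussion with the Study Physician limits variation between sites, and Section 8.1.3.1 leads an investigator to Appendix K despite the wrong reference. Both points reduce the practical effect. Neither tells the Study Physician which section governs.

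A reader might also infer that every patient who progresses on drug is affected, or that extra exposure has no limit. Neither follows. The rules part only for those judged to benefit, and the planned 2 years, toxicity, new therapy and withdrawal of consent remain as limits on dosing, with longer treatment offered only to responders.

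**Conclusion.** The conflict holds, with limited reach. One rule on dosing at progression cannot be derived from the documents, and the Appendix J reference is wrong in both 6.6.6.7 and 7.1. The conclusion rests on reading 6.6.6.7 together with its heading, and on the absence of any text linking it to 7.1.

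The effect falls on safety and exposure summaries, deviation classification and, indirectly, OS, in an unstated number of progressing patients judged to benefit. A reader might infer that the Part B primary endpoint or PFS is at risk; the definitions cut off at progression, so it is not. No hypothesis test is planned (Protocol 9.1), so no error rate is involved. The point should be corrected because it concerns who is dosed after progression and the repair is cheap. It is not a flaw in the primary analysis.

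**What to change.** - Reconcile Protocol 6.6.6.7, 7.1, the synopsis, 10.4.1, 10.6.6.2 and SAP 8.2 into one rule on dosing at progression. Which clinical rule applies is the sponsor's choice.
- State what confirmed means in 7.1, and use the same term wherever the rule appears.
- Replace the Appendix J reference with Appendix K in 6.6.6.7 and 7.1.
- If the chosen rule lets some patients continue, say how benefit is judged, what assessments follow progression, and that such dosing is not a deviation under SAP 4.3.7.

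The cost is wording in a protocol amendment and a matching line in the SAP. The definitions of ORR, DoR, PFS and OS, and the sample size, need not change.
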